6.2 Magnetic Resonance Imaging

The Rheumatoid Arthritis Magnetic Resonance Imaging Scoring System (RAMRIS), developed initially by the Outcome Measures in Rheumatology Clinical Trials (OMERACT) international working group in 1998, assesses synovitis, bone marrow edema (osteitis) and erosions of the wrist and metacarpophalangeal (MCP) joints. Magnetic resonance imaging (MRI) is sensitive and rapidly responsive to change. Although not predictive at the individual subject level, MRI is effective in predicting structural disease response to therapeutic

interventions for groups, and can be used to guide dose selection for larger radiographic progression studies.

In a 20-subject cohort of early RA patients, an attempt to induce remission with MTX or MTX with infliximab showed no difference in van der Heijde Modified Total Sharp Scores (vdHmTSS) after 1 year (change of 10 vs. 12, respectively). However, MRI in the infliximab group showed improvement in bone marrow edema (osteitis) (P<0.05) by Weeks 4 and 14, which was predictive for no new MRI erosions in the infliximab group at 1 year (P = 0.0125vs. MTX alone).²² Even in treated subjects in clinical remission or with low clinical disease activity. MRI progression occurs, and baseline bone marrow edema (osteitis) was predictive for new erosions by MRI over the ensuing year.²³ In a Phase 2 study of golimumab and MTX, compared to MTX ('GO-BEFORE'), the concurrent MRI data in a subset of 318 subjects at Weeks 12 and 24 showed significantly lower RAMRIS erosion scores with golimumab (P = 0.016 and P = 0.010 vs. MTX alone at Weeks 12 and 24, respectively). In comparison, X-rays in the MRI cohort were underpowered at Week 28, but the full 637-subject X-ray data showed significant vdHmTSS benefit at that time point.²⁴ Highlighting the independent processes of synovitis and bone resorption in RA¹⁵, the anti-RANKL monoclonal antibody denosumab showed decreased erosion progression at month 6 by both MRI (P = 0.007 vs. placebo) and X-ray (P = 0.019), without alterations in synovitis.²⁵

6.3 Janus Kinases

Cytokines play pivotal roles in inflammation, and targeting either cytokines or their receptors are effective approaches to treating RA. Type 1 and 2 cytokine receptors associate with Janus kinases (JAKs) to affect intracellular signaling. ²⁶ These structurally unique tyrosine protein kinases play an essential role in immune cell development and function. One JAK, JAK3, has particularly selective functions. JAK3 is an integral part of the signaling pathway used by γ chain cytokine receptors (the interleukin-2 family: IL-2, IL-4, IL-7, IL-9, IL-13, IL-15, IL-21). ^{26,27,28} Upon stimulation of the cytokine receptor by ligand (cytokine) binding, the receptors oligomerize, facilitating tyrosine phosphorylation of JAK3 and subsequent signal transduction via the signal transducers and activators of transcription (STAT). Expression of JAK3 is confined to the lymphohematopoietic system, while the other members of the JAK family (JAK1, JAK2, and tyrosine kinase 2) are more broadly expressed. ^{27,29,30} Mutations of the interleukin receptor γ chain underlie X-linked severe combined immunodeficiency (SCID), indicative of its critical role in the development and function of lymphocytes, and mutations of the downstream JAK3 are responsible for some cases of autosomal recessive SCID. ²⁸

6.4 VX-509

VX-509 is a potent small-molecule inhibitor of JAK3 in development as a potential treatment for subjects with active RA and other autoimmune diseases. In Phase 2a Study VX09-509-101 (Study 101), VX-509 demonstrated significant activity in reducing signs and symptoms of RA over 12 weeks in subjects not receiving concurrent DMARDs. Additionally, other generalized JAK inhibitors are in development for RA. Findings from these studies resulted in rapid, statistically significant reductions in the signs and symptoms

of RA; however, the effect on progression of erosive disease at 24 weeks in a study with a placebo control arm for 3 months was uncertain (P<0.05 with significant contribution by outliers). ^{34, 35}

The VX-509 Investigator's Brochure provides specific details about the completed nonclinical and clinical VX-509 studies and a full description of safety findings.³⁶ No safety issues have been identified in studies in RA patients and normal healthy volunteers that would preclude the dosing regimens proposed for the present study; however, this study is the first study in RA subjects receiving a DMARD to evaluate concurrent treatment with VX-509 300 mg daily (qd) for 12 weeks.

6.5 Rationale for the Present Study

The current study is designed to evaluate the safety and efficacy across doses of VX-509, including MRI imaging, in subjects with active RA who have had an inadequate response to DMARD. Information on early MRI response with the evaluated VX-509 doses in this trial will be utilized to help select appropriate dose(s) for a subsequent pivotal trial evaluating radiographic progression. Evaluation of synovial tissue pre- and post-VX-509 administration in a subset of the study subjects will provide further information concerning the JAK3-based mechanism of action of VX-509, within the target tissue, and concerning any alteration in the osteoclastogenic/resorptive synovial environment following VX-509 administration.

7 STUDY OBJECTIVES

7.1 Primary Objectives

During 12 weeks of treatment in subjects with active RA on stable DMARD therapy:

- To evaluate the efficacy of VX-509 across a range of doses
- To evaluate the early effect of VX-509 administration on joint structures as assessed by MRI

7.2 Secondary Objectives

During 12 weeks of treatment in subjects with active RA on stable DMARD therapy:

- To evaluate major arthritis improvement with VX-509 administration across a range of doses
- To evaluate changes in RA physical function
- To evaluate changes in physical and mental health-related quality of life
- To investigate the pharmacokinetics (PK) of VX-509 and its metabolite in plasma
- To evaluate the safety of VX-509

7.3 Other Objectives

During 12 weeks of treatment in subjects with active RA on stable DMARD therapy:

- To evaluate the predictive value of MRI response for other efficacy parameters
- To evaluate change in health-related quality of life
- To investigate biomarkers reflecting bone turnover and inflammation during VX-509 administration
- To determine the PK/pharmacodynamic (PD) relationships between plasma exposure to VX-509 and its metabolite and efficacy, safety, and plasma biomarkers

After 4 weeks of treatment in subjects with active RA on stable DMARD therapy (Synovial Biopsy Subset only):

- To investigate the immunomodulatory and anti-resorptive effects in the joint of VX-509 administration
- To determine the PK/pharmacodynamic (PD) relationships between plasma exposure to VX-509 and its metabolite and biomarkers in the joint

8 STUDY ENDPOINTS

8.1 Primary Endpoints

- Proportion of subjects who achieve ≥20% improvement in disease severity according to the American College of Rheumatology criteria (ACR20), using C-reactive protein (CRP) (ACR20-CRP) at Week 12.
- Change from baseline in Disease Activity Score 28 using CRP (4-component) (DAS28-4[CRP]) at Week 12.
- Change from baseline in Outcome Measures in Rheumatology Clinical Trials (OMERACT) Rheumatoid Arthritis Magnetic Resonance Imaging Scoring System (RAMRIS) synovitis score in designated hand (minimal assessed joints: wrist, MCP joints #2 to #5) at Week 12.
- Change from baseline in OMERACT RAMRIS bone marrow edema (osteitis) in designated hand (minimal assessed joints: wrist, MCP joints #2 to #5) at Week 12.
- Change from baseline in OMERACT RAMRIS erosion score in designated hand (minimal assessed joints: wrist, MCP joints #2 to #5) at Week 12.

8.2 Secondary Endpoints

- Proportion of subjects who achieve ACR50-CRP and ACR70-CRP responses at Week 12.
- Proportion of subjects with DAS28-4(CRP) <2.6, and those who achieve a remission, moderate response or good response according to the European League Against Rheumatism (EULAR) response criteria at Week 12.
- ACR hybrid scores at Week 12.

- Change from baseline in Health Assessment Questionnaire –Disability Index (HAQ-DI) at Week 12.
- Change from baseline in the Physical Function subscale of the 36-item Short Form (SF-36) at Week 12
- Change from baseline in the Physical Component and Mental Health Components of the SF-36 at Week 12
- Change from baseline in OMERACT RAMRIS synovitis, bone marrow edema (osteitis), erosion scores at Week 6.
- PK parameters of VX-509 and its metabolite in plasma (maximum observed concentration $[C_{max}]$ and area under the concentration versus time curve [AUC]).
- Safety and tolerability as indicated by adverse events, laboratory tests, electrocardiograms (ECGs) and vital signs.

8.3 Other Endpoints

- Predictive value of RAMRIS responses at Weeks 6 and 12 on DAS28-4(CRP) and ACR20-CRP at Week 12.
- Change from baseline in OMERACT RAMRIS joint space narrowing score at Weeks 6 and 12.
- Change from baseline in the Clinical Disease Activity Index (CDAI), CDAI moderate and low disease activity, and CDAI remission at Week 12.
- Change from baseline in the remaining 7 subscales of the SF-36 at Week 12.
- Change from baseline in blood biomarkers including markers of bone turnover, cytokines, and other biomarkers.
- Proportion of subjects who achieve ACR20, ACR50, and ACR70 assessed using erythrocyte sedimentation rate (ACR20-ESR, ACR50-ESR, and ACR70-ESR) responses, at Weeks 6 and 12.
- PK/PD relationship for plasma PK parameters and arthritis efficacy including RAMRIS, safety and plasma biomarkers.

Synovial Biopsy Subset only:

- Change from baseline at Week 4 in synovial biomarkers including histologic evidence of JAK3 activation, of osteoclast recruitment, level of monocellular infiltrate, and other biomarkers.
- PK/PD relationship for plasma PK parameters and synovial biomarkers.

9 STUDY DESIGN

9.1 Overview of Study Design

This is a Phase 2, randomized, placebo-controlled, double-blind, dose-ranging, multicenter study of VX-509 in subjects with moderate to severe RA who are seropositive or have demonstrated erosive disease, and an inadequate response to a DMARD.

Subjects who have been on a stable dose of DMARD (Section 10.3) must have a swollen joint count of ≥ 6 out of 66 assessed joints and a tender joint count of ≥ 8 out of 68 assessed joints, and a CRP level $\geq 1.2 \times$ the upper limit of normal (ULN) or Westergren erythrocyte sedimentation rate $\geq 1.2 \times$ ULN to qualify for the trial. MRI of the most swollen hand (2+ synovitis of wrist or ≥ 2 MCPs) at baseline will be performed before dosing and at Weeks 6 and 12. A subset of approximately 6 (no more than 10) subjects will undergo arthroscopic synovial biopsies before the first dose at baseline (Day 1) and at Week 4 (Synovial Biopsy Subset).

Subjects will be randomized with stratification based on prior use of biological response modifiers (including a tumor necrosis factor [TNF] inhibitor). VX-509 will be coadministered with DMARD for a planned duration of 12 weeks. Approximately 40 subjects will be randomized to 1 of 4 dosing regimens at a 1:1:1:1 ratio. VX-509-matched placebo tablets will be used to maintain the double-blind. As an exception, the subjects in the Synovial Biopsy Subset will only be randomized to the 200 mg qd dose of VX-509 (Arm C). Subjects in the Synovial biopsy Subset will know that they are not receiving placebo, but not the dose they are receiving.

Arm A. Placebo (N = 10)
Arm B. 100 mg VX-509 qd (N = 10)
Arm C. 200 mg VX-509 qd (N = 10)
Arm D. 300 mg VX-509 qd (N = 10)

The protocol has optional interim analyses (IA) for the purpose of selecting appropriate dose(s) for a subsequent pivotal trial (Section 13.3.4.7). No changes in study design or conduct will be made based on the results of an IA.

9.1.1 Screening

Procedures to be performed during the Screening Visit are listed in Table 3-1.

The Screening Visit will occur within 28 days before administration of study drug to confirm that subjects meet the selection criteria. The investigator (or an appropriate authorized designee at the investigator site) will obtain written informed consent from each subject before conducting any study related assessments or procedures.

Subjects who fail screening initially may be rescreened 1 additional time within 30 days of the initial Screening Visit. Subjects who fail screening because of abnormal safety laboratory results or CRP/WESR are not required to complete the entire Screening Visit for their rescreening, and may rescreen by testing just those laboratory abnormalities.

9.1.2 Treatment Period

Procedures to be performed during the Treatment Period are listed in Table 3-2.

After verifying subjects are eligible according to the inclusion and exclusion criteria on Day 1, subjects will be randomized to the dosing groups described in Section 9.1.

Dosing details are given in Section 11.2.

9.1.3 Safety Follow-up

All subjects will have a Safety Follow-up Visit 28 (\pm 7) days following the last dose of study drug, and the procedures as listed in Table 3-2 will be completed.

9.1.4 Early Discontinuation

Subjects who prematurely discontinue treatment in this study for any reason will be asked to return to the clinical research unit for the Week 12/Early Termination of Study Treatment Visit (Table 3-2). If the subject discontinues before completing 3 weeks of treatment, the MRI will not be repeated.

Stable background NSAIDs and low dose corticosteroid treatment are allowed in this study. Analgesics, both narcotic and non-narcotic, are allowed during the trial with the exception of the period before joint assessments (Section 10.3). It is anticipated that these factors will serve to limit withdrawals for inadequate control of disease activity over 12 weeks. If the investigator determines that the only mechanism to control disease activity in this period would be to perform an arthrocentesis with or without an intraarticular injection, this proposal (as opposed to early treatment discontinuation) should be discussed first with the medical monitor.

Discontinuation of study drug administration will be considered for subjects with, but not limited to, the occurrence of 1 or more of the abnormalities listed below:

- Aspartate aminotransferase (AST) and/or alanine aminotransferase (ALT) levels and/or alkaline phosphatase levels that increase $\ge 3 \times \text{ULN}$ (see Section 12.9.3)
- Lymphocytes < 0.5 K/μL
- Absolute neutrophils <1.0 K/μL
- Platelets <100 K/μL
- Hemoglobin ≤8 g/dL

Subjects who prematurely discontinue treatment in this study for any reason will complete the Week 12/Early Treatment Termination assessments. Subjects who withdraw will be asked to return to the site, if they consent, for the Safety Follow-up Visit at $28 (\pm 7)$ days after their last dose of study drug. The assessments to be conducted during the Safety Follow-up Visit are listed in Table 3-2.

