10.2 Exclusion Criteria

Subjects who meet any of the following exclusion criteria will **not** be eligible for this study:

- 1. Inflammatory and rheumatological disorders other than RA, where arthritis may be a prominent feature, such as systemic lupus erythematosus, mixed connective tissue disease, scleroderma, poly/dermatomyositis, or gout; secondary Sjogren's syndrome or interstitial lung disease are allowed.
- 2. History of any illness that might confound the results of the study or pose an additional risk in administering study drug(s) to the subject. This may include, but is not limited to, history of cardiovascular or central nervous system disease, history or presence of clinically significant abnormalities on physical exam, ECG or laboratory examination, or history of clinically significant psychiatric or mental disease.
- 3. History of cancer, except squamous or basal cell cancers of the skin or in situ cancer of the cervix.
- 4. History of hematologic disorders including neutropenia and thrombocytopenia other than Felty's syndrome.
- 5. History of tuberculosis (TB), regardless of history of anti-mycobacterial treatment; or active TB as determined by X-ray, TB skin test and QuantiFeron® TB Gold Assay (QuantiFeron assay). If the subject has a hypersensitivity to skin test preparation associated with the TB skin test then the QuantiFeron alone is acceptable.
- 6. Acute or chronic active infection requiring systemic antimicrobial treatment with the exception of onychomycosis receiving antifungal medication, or acne and rosacea receiving low-dose antibiotics.
- 7. History of febrile illness within 5 days before the first dose of study drug.
- 8. History of previous osteomyelitis, infected joint or joint prosthesis.

- 9. Subjects who are at high risk of developing an infection due to a compromised immune system including poorly controlled diabetes.
- 10. Weight <45 kg at screening.
- 11. A 12-lead ECG demonstrating QT interval corrected (QTc) >450 msec at the screening Visit. If QTc exceeds 450 msec, the ECG should be repeated 2 more times, and the average of the 3 QTc values used to determine the subject's eligibility. Subjects should also be excluded if any other clinically significant interval (e.g., PR prolongation), morphologic (e.g., T-wave inversion), or conduction abnormalities are observed.
- 12. Planned surgery during the study.
- 13. Metal implant or other contra-indication to MRI scanning.

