- 25. Subjects who require concomitant use of any moderate or strong inhibitors or inducers of CYP3A or P-gp or who require CYP3A substrates with serious associated side effects at high exposure (Section 10.3; partial lists in Section 16.3).
- 26. Have received a live or live attenuated vaccination in the 4 weeks before study Day 1.
- 27. Positive urine or serum pregnancy test.
- 28. Hemoglobin <11 g/dL for females or <12 g/dL for males at screening.
- 29. Absolute neutrophil count <1.5 K/μL at screening.
- 30. Platelet count <120 K/μL at screening.
- 31. ALT or AST \geq 1.5 × the ULN at screening.
- 32. Creatinine clearance <30 mL/min at screening
- 33. Positive hepatitis B surface antigen, hepatitis C virus antibody, or human immunodeficiency virus 1 and 2 antibodies at screening.
- 34. Other clinically significant out-of-range laboratory results in hematology, serum chemistry, coagulation studies, or urinalysis at the screening as judged by the investigator.

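### Lymphocytes are the only blood count on the Section 9.1.4 stopping list with no numeric screening limit in Section 10.2, so a subject already at the listed value can be randomised

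*Protocol*

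**What the plan says.** Section 9.1.4 introduces its list of laboratory abnormalities with "Discontinuation of study drug administration will be considered for subjects with" one or more of them. The list is stated not to be exhaustive. It covers AST, ALT and "levels and/or alkaline phosphatase levels that increase" to 3 × ULN or more, "Lymphocytes < 0.5 K"/µL, neutrophils below 1.0 K/µL, platelets below 100 K/µL, and hemoglobin of 8 g/dL or less.

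Section 10.2 gives numeric screening exclusions for several of the same tests:

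- exclusion 28: "Hemoglobin <11 g/dL for females or <12 g/dL for males at screening"
- exclusion 29: "Absolute neutrophil count <1.5 K"/µL
- exclusion 30: "Platelet count <120 K"/µL
- exclusion 31: ALT or AST at or above 1.5 × ULN

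No exclusion gives a lymphocyte value. The criteria that could reach a low count are qualitative. Exclusion 34 covers "Other clinically significant out-of-range laboratory results in hematology, serum chemistry, coagulation studies, or urinalysis at the screening as judged by the investigator". Exclusion 2 includes "history or presence of clinically significant abnormalities on physical exam, ECG or laboratory examination". Exclusion 4 concerns a history of hematologic disorders and names neutropenia and thrombocytopenia. Exclusion 9 concerns high infection risk from a compromised immune system. Exclusion 22 requires recovery from cytopenias, but only after a depleting antibody.

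**The concern.** The Section 9.1.4 lymphocyte trigger is an absolute count, not a fall from baseline. A subject who enters at, say, 0.4 K/µL meets the listed value before the first dose. For the other three blood counts the entry limit rules this out at screening. For lymphocytes the decision rests on each investigator's judgement, so two sites may decide differently on the same count.

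Lymphocytes are also the count most closely tied to the drug's target. Section 6.3 says that JAK3 is expressed only in the lymphohematopoietic system and that JAK3 mutations account for some severe combined immunodeficiency. Subjects take a background DMARD and may take up to 10 mg/day of prednisone (Section 10.3). Section 9.2.2 describes this as the first RA study of 300 mg once daily with a DMARD for 12 weeks, and Section 13.3.4.7 says there is no Data Monitoring Committee. In that setting a subject should not start dosing at a level that the protocol already regards as a reason to think about stopping.

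**Working it through.** No sample size, power or error-rate figure is involved. The check is a line-by-line comparison of Section 9.1.4 with Section 10.2.

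| Test | Stopping considered (9.1.4) | Excluded at screening (10.2) | Distance between the two |
|---|---|---|---|
| AST, ALT | ≥3 × ULN | ≥1.5 × ULN (31) | 3 − 1.5 = 1.5 × ULN |
| Alkaline phosphatase | ≥3 × ULN | no number | not defined |
| Lymphocytes | <0.5 K/µL | no number | not defined |
| Neutrophils | <1.0 K/µL | <1.5 K/µL (29) | 1.5 − 1.0 = 0.5 K/µL |
| Platelets | <100 K/µL | <120 K/µL (30) | 120 − 100 = 20 K/µL |
| Hemoglobin | ≤8 g/dL | <11 (women) or <12 (men) g/dL (28) | 11 − 8 = 3, or 12 − 8 = 4 g/dL |

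1. Counting AST and ALT separately, Section 9.1.4 names seven analytes. Five have a stricter numeric entry limit and two do not (alkaline phosphatase and lymphocytes).
2. Of the four blood counts, three have an entry limit. Lymphocytes is the only one without. Alkaline phosphatase is not a blood count, and its trigger is worded as a rise.
3. The qualitative exclusions, applied to a screening count of 0.4 K/µL:
   - Exclusion 34 applies only if the investigator judges the result clinically significant.
   - Exclusion 2 needs the same judgement.
   - Exclusion 9 applies only if the subject is judged to be at high infection risk from immune compromise.
   - Exclusion 4 needs a history of a hematologic disorder. Lymphopenia is not named, although the wording is not exhaustive.
   - Exclusion 22 applies only after a depleting antibody.
4. None of these forces exclusion on the count. If the investigator judges the value not clinically significant and no other criterion applies, randomisation is within protocol.
5. The information needed for a numeric rule is already collected. Lymphocytes are in the hematology differential (Table 12-1), and hematology is drawn at the Screening Visit (Table 3-1).

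**The case against.** The strongest reply is that nothing here is an error. The protocol nowhere promises that every Section 9.1.4 value has a matching entry number, alkaline phosphatase has none either, and the list only prompts consideration. The word used there for the abnormalities arising could also be read as new onset. This stands as far as it goes: a reader might infer that Sections 9.1.4 and 10.2 contradict each other, and they do not. What remains is that the sponsor did not leave the other three blood counts to judgement, and the protocol gives no reason for treating lymphocytes differently.

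A second reply is that entry is already controlled. Exclusion 34 expressly reaches hematology, exclusion 9 addresses the very risk at issue, and most investigators would hesitate over a count on the stopping list. That makes such an entry possible rather than likely. It does not make it a deviation.

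A third concerns interpretation. A reader might infer that a low Week 2 count in such a subject would be misread as a drug effect. The documents largely deal with this. Section 13.3.4 takes the last value before the first dose as baseline. Section 13.3.4.2 plans changes from baseline, shift tables by normal range and toxicity grade, and lymphocyte change plots, and there is a placebo arm. Only the site's immediate handling of the trigger in that subject stays awkward.

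Finally, a reader might take the five infection SAEs in Section 9.2.5, all in subjects on VX-509, as evidence of harm from low lymphocytes. They cannot carry that. Section 9.2.5 gives no lymphocyte data, four of the five groups in that study received active drug, and infections overall were reported in about 17% of both placebo and VX-509 subjects, though more often at higher doses. How many subjects the five events came from is not stated. They say nothing about where an entry limit should lie.

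**Conclusion.** The gap is confirmed on the text. Lymphocytes are the one blood count of four on the stopping list without a numeric screening limit, and a subject already below 0.5 K/µL can be randomised without a deviation if the investigator so judges. It is a safety misalignment that rests on the drug's mechanism and the protocol's own trigger value. It is neither a contradiction nor a sign of observed harm.

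Its practical size is unknown. The documents do not give the share of screened subjects below 0.5 K/µL, and the study has only about 40 subjects. No power figure, estimate or test is affected. The conclusion assumes that the trigger is read as an absolute level, as written, and that no exclusion outside those discussed above sets a lymphocyte value. The comparison is certain; how often such a subject would present is not.

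**What to change.** Add one exclusion to Section 10.2: absolute lymphocyte count below 0.5 K/µL at screening. Treat this as the minimum. A limit equal to the trigger leaves no margin: a subject at exactly 0.5 K/µL would still enter and could cross it through ordinary variation, and since screening may be up to 28 days before dosing, the count could already be lower on Day 1. The sponsor's clinicians may therefore prefer a higher limit, as they chose for neutrophils, platelets and hemoglobin. The documents give no basis for naming that number here.

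The cost is one line in the next amendment and no new test. The downside is a probably small but unknown number of extra screen failures. Section 9.1.1 softens this: a subject who fails on a safety laboratory result may be rescreened once within 30 days by repeating only the abnormal test.
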